**Dependent variables:**

Neuroimaging: resting-state fMRI; arterial spin labeling (ASL); task-based fMRI (monetary incentive delay)

Immune Markers: Plasma CRP

**Objective 2: To examine whether L-DOPA-mediated increases in corticostriatal connectivity are associated with improvement in objective measures of motivation and motor performance.**

**Hypothesis 2:** L-DOPA administration will be associated with improvement in motivation and psychomotor speed compared to placebo, and will correlate with increased corticostriatal connectivity.

Patients described in Objective 1 will undergo performance-based assessments of motivation and motor performance, and self-report assessments of depressed mood, including anhedonia, following administration of L-DOPA and placebo, which will be correlated with changes in functional connectivity.

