**Dependent variables:**

Neuropsychology:	Finger Tapping Task; Reaction Time Task (CANTAB); Trail Making Test, Part A; Digit Symbol Test; Effort Expenditure Rewards Task (EEfRT)
Self-report:	Snaith-Hamilton Pleasure Scale (SHAPS); Inventory of Depressive Symptoms-Self Report (IDS-SR); Beck Depression Inventory (BDI) Anhedonia Subscale; Multidimensional Fatigue Inventory (MFI); Profile of Mood States (POMS); State-Trait Anxiety Inventory (STAI) State Scale

**Objective 3: To determine whether peripheral and central cytokines and/or biomarkers of decreased dopamine synthesis predict connectivity and behavior before and after L-DOPA challenge.**

*Hypothesis 3:* Increased biomarkers of central and peripheral inflammation, and decreased cerebrospinal fluid (CSF) dopamine, its precursors and metabolites, will correlate with and predict greater fMRI and behavioral responses to L-DOPA

Patients described in Objectives 1 and 2 will undergo

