**Gender and Minorities:** Based on the composition of the patients treated for major depression at the Emory Clinic, Grady Health System, VAMC and community psychiatry clinics, we anticipate that an equal number of men and women will be included in the study. As for the racial composition of the sample, we anticipate 30-40% African Americans, 5-10% Latinos and 2-5% Asians, which is reflective of the community (city of Atlanta) from which our sample will be drawn.

**Dropouts:** Because participation in this study involves two screening visits followed within approximately 2 weeks by three study visits, we anticipate that there will be few subjects who will drop out between screening and the study visits. In our experience, however, there will be subjects who will have to be removed from the study because of a positive urine toxicology screen. In addition, some subjects may become too severely depressed and/or suicidal between enrollment and completion of the study. Given a conservative estimate of a 20% screen failures and 20% dropout rate, we will need to recruit ~ 225 subjects to reach the target of 80 subjects for analysis. Psychiatric staff is available throughout each subject's participation, and can provide on-site emergency care in the event of crisis.

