**Epworth Sleepiness Scale (ESS)** will be used to assess subjective sense of daytime alertness (79). The ESS is a widely used measure of self-reported alertness. The ESS is a 24 point scale, with 8 different items for which the patient rates the likelihood of falling asleep on a 0-3 scale. Higher scores signify a greater likelihood of daytime sleepiness. The ESS has been reported to distinguish conditions characterized by excessive daytime sleepiness (i.e., narcolepsy, sleep apnea) from control populations (79).

**Pittsburgh Sleep Quality Index (PSQI)** will be used to assess sleep quality over the past month and can be used to distinguish good sleepers from bad sleepers (80). The scale contains 15 multiple-choice items that inquire about frequency of sleep disturbances and subjective sleep quality and 4 write-in items that inquire about typical bedtime, wake-up time, sleep latency, and sleep duration. The PSQI generates seven scores that correspond to relevant domains of sleep, and each score ranges from 0 (no difficulty) to 3 (severe difficulty). The component scores are summed to produce a global score (range of 0-21). A PSQI global score >5 is considered to be suggestive of significant sleep disturbance (80).

**Snaith-Hamilton Pleasure Scale (SHAPS)** is a 14-item scale used to assess present-state hedonic tone (81). The items 1, 4, 8 and 9 refer to interests, items 3 and 10 to food and drink, items 2, 7, 13 and 14 to social interaction and items 5, 6, 11 and 12 to sensory experiences.

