**Childhood Trauma Questionnaire (CTQ):** The CTQ is a self-report inventory assessing 3 types of childhood abuse: sexual, physical, and emotional. Studies have established the internal consistency, stability over time, and criterion validity of both the original 70-item CTQ and the current brief version (82). The CTQ yields a total score and subscale scores for each of the types of child abuse. CTQ data from Emory have demonstrated good internal consistency reliability (alpha = .99 for physical abuse; alpha = .94 for sexual abuse; alpha = .93 for emotional abuse; and alpha = .98 for the total of these 3 scales). The data from the CTQ will be used to classify subjects into 2 categories for each type of abuse (physical, sexual, and emotional): (1) those with CTQ scale scores in the none to mild range, and (2) those with CTQ scores in the moderate to severe range. We will then create a composite variable across all of the 3 types of abuse. Using this composite, we can divide participants into 2 groups with respect to the numbers of types of abuse that fall into the moderate to severe

range: (1) those with no type of abuse in the moderate to severe range, and (2) those with at least 1 type of abuse in the moderate to severe range (83).

**Habits:** The Habits form is a brief questionnaire that assesses a subject's daily smoking, daily caffeine consumption, and exercise patterns.

**Beck Depression Inventory, 2nd edition (BDI-II), Anhedonia Subscale** is a subscale of the 21-item self-report measure of depressive symptoms, rated on a 4-point Likert scale based on the patient's experience in the last two weeks.

**Profile of Mood States (POMS)** is a psychological rating scale used to assess transient, distinct mood states. Participants rate the extent to which they feel: unhappy, blue, lonely, gloomy, and worthless on a scale from 0 (not at all) to 4 (extremely).

**Post-traumatic Stress Disorder Symptom Scale (PSS):** The PSS is a 17-item self-report scale that assesses the presence and severity of symptoms related to a single identified traumatic event in individuals with a known trauma history.

**Perceived Stress Scale** is a self-report scale measuring the perception of stress. The items are designed to predict how uncontrollable, unpredictable, and overloaded the subjects find their lives.

**Visual Analog Scale of Pain:** is a scale between the range of 1 to 10, that measures the perception of pain.

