**Staging System for Reproductive Aging and Menopause Rating Scale (MRS)** is an 11-item self-report scale that assesses the presence and severity of symptoms related to menopause including psychiatric and physical symptoms. This form will be administered to female subjects only.

**Columbia-Suicide Severity Scale:** The Columbia-Suicide Severity Rating Scale (C-SSRS) is a fully-structured, clinical interview designed to systematically query patients regarding past and current suicidal ideation and behavior (SIB) (100). The psychometric characteristics of the patient- reported C-SSRS have been assessed in multiple contexts. It has well validated to elicit suicidal ideas in depressed subjects and will be consequently used to identify individuals experience acute severe depressive symptoms and refer them for immediate treatment.

**Post-Traumatic Stress Disorder Checklist for DSM-5 (PCL-5):** The PCL-5 is a 20-item self-report measure that assesses the 20 DSM-5 symptoms of PTSD, rated on a 5-point Likert scale based on the patient's experience in the last month.

**Beck Anxiety Inventory (BAI):** The BAI is a 21-item self-report measure of anxiety symptoms, rated on a 4-point Likert scale based on the patient's experience in the last month.

**Motivation and Pleasure Scale (MAP):** The motivation and pleasure questionnaire is an 18-item self-report inventory that was created to disentangle state-wise motivational and consummatory components of everyday activities over a 24-hour period, and has been previously validated as a measure of reward-related symptoms in psychiatric populations. This scale will be used to assess self-reported changes in symptoms of anhedonia before and after inflammation blockade.

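### BDI Anhedonia, an Objective 2 response outcome, rates the last two weeks and so is effectively insensitive to a single dose assessed within one visit

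*Combined protocol and SAP*

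**What the plan says.** Section 4, Objective 2, plans "self-report assessments of depressed mood, including anhedonia, following administration of L-DOPA and placebo", to be correlated with the change in connectivity. The listed self-report dependent variables include the "Beck Depression Inventory (BDI) Anhedonia Subscale" alongside SHAPS, IDS-SR, MFI, POMS and STAI State.

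Section 7, Analytic Strategy for Objective 2, enters post-administration self-report scores into linear models that control for pre-administration scores. It also compares post-minus-pre differences under L-DOPA and placebo by paired t test, and relates connectivity change to relevant post-dose self-reports.

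The Self-report questionnaires part of section 5 gives the time frames. BDI Anhedonia is "rated on a 4-point Likert scale based on the patient's experience in the last two weeks". SHAPS is described as a present-state measure, POMS as covering transient moods, and STAI State as covering current anxiety. The Motivation and Pleasure scale (MAP) covers "state-wise motivational and consummatory components of everyday activities over a 24-hour period", and its stated use refers to change around inflammation blockade. MAP is in the visit battery in the footnotes to the procedures table, but not in the Objective 2 list.

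Treatment is one tablet per visit (section 10), and each visit lasts about 5 to 6 hours (section 5, Study Visit 1 & 2).

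**The concern.** A scale that asks about the past fortnight is being used to detect a change that could only have begun a few hours earlier. A patient who follows the instructions rates almost the same fortnight before and after the tablet, so the within-visit difference should be close to zero whatever L-DOPA does. The comparison of post-dose scores between the L-DOPA and placebo visits has the same weakness, because only a sliver of either window follows the dose.

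What is at stake is interpretation. Section 4 lists BDI Anhedonia beside SHAPS without ranking them. A null on BDI Anhedonia could be taken as evidence that L-DOPA leaves anhedonia unchanged, and a difference significant at 0.05 by chance could be taken as a response. The scale can support neither reading.

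**Working it through.** The plan states no effect size, sample size or power for any self-report, so there is no figure of its own to reproduce. Its one power statement (section 7: dz about 1, n=30 per group, above 80%) concerns connectivity.

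**Inputs**
- BDI Anhedonia window: two weeks = 14 × 24 = 336 h (section 5, Self-report questionnaires).
- MAP window: 24 h (same place).
- Visit length: at most about 6 h (section 5, Study Visit 1 & 2).
- Scans from about 09:00, post-scan testing about 12:30 to 14:00 (section 5, Study Overview).
- Pre-dose scan: 25 to 35 min (Study Visit 1 & 2). The clock time of the dose is not stated; I infer about 09:25 at the earliest and take 10:00 as a later case.

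**1. Overlap of the pre- and post-dose windows.** Two 336 h windows ending h hours apart share (336 − h)/336. With h = 6, the longest possible gap within a visit, this is 330/336 = 98.2%. Any shorter gap gives more overlap.

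**2. Share of the BDI window after the dose.**
- Longest: 09:25 to 14:00 = 4.58 h; 4.58/336 = 1.4%.
- Shorter case: 10:00 to 12:30 = 2.5 h; 2.5/336 = 0.7%.

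This share applies to the between-visit contrast as well as the within-visit difference, and does not depend on the interval between visits.

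**3. What that does to a test (illustration only).** Suppose a rating is a time-weighted average over its window, so that observed dz = share × true dz. Borrow a true momentary dz of 1 from the connectivity assumption. For 2.5 to 4.5 h after the dose, observed dz is 0.007 to 0.013. A two-sided paired t test at 0.05 then has power of 5.0% to 5.2% for n between 27 (one CRP group) and 80 (about the whole sample). That is the type I error rate and little more.

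**4. MAP by the same method.** The share is 2.5/24 = 10% to 4.58/24 = 19%. For 2.5 to 4.5 h and a true dz of 1, observed dz is 0.10 to 0.19, with power 8% to 16% at n=27 and 15% to 38% at n=80. MAP is heavily diluted, but not blind to the dose.

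**5. Timing of the forms.** The Study Overview in section 5 places the self-reports in the morning, listed ahead of the scans and dose, and names only blood sampling and neurocognitive testing after the scans. The Study Visit 1 & 2 text mentions mood questionnaires without a time. Objective 2 and its analysis need post-dose scores. If the Study Overview governs, no self-report, state scales included, can register the dose.

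**The case against.** The best defence is that little depends on this subscale. Hypothesis 2 says that "L-DOPA administration will be associated with improvement in motivation and psychomotor speed compared to placebo", and the objective's title refers to objective measures. BDI Anhedonia is one of 11 listed dependent variables in a self-described pilot, and a present-state anhedonia scale stands in the same list. The connectivity analysis is also limited to relevant responses. This stands, and it makes the point minor. It does not make a two-week scale suitable for a same-day difference.

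A second defence is that patients may not average over time as instructed and may let their present mood colour the answer. The documents give no data on this. If it happens, the score departs from the scale's own instruction, which is no basis for an outcome.

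Four stronger readings are tempting, and the documents do not support them:
- **That MAP is an Objective 2 outcome that must be null.** It is not in the section 4 list, it is described as state-wise, and part of its window would follow the dose.
- **That the two visits' BDI windows overlap by a known amount.** The Dropouts paragraph says "two screening visits followed within approximately 2 weeks by three study visits", which can mean only that the visits begin by then. Section 9 allows up to 4 weeks from consent to the final assessment, and no interval between Visits 1 and 2 is given. With 14-day windows d days apart the overlap is (14 − d)/14, so 50% at 7 days and 86% at 2 days, but both intervals are assumptions.
- **That the recall and state scales are pooled, so that one dilutes the other.** Section 7 describes no composite score.
- **That IDS-SR and MFI share the fault.** The documents give no recall period for either.

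**Conclusion.** The point holds for BDI Anhedonia: at least 98% of its window is common to the pre- and post-dose ratings, and at most about 1.4% follows the dose. These figures rest on the protocol's two-week description, the 6 h upper limit on the visit and, for the second, an inferred dose time of about 09:25; a later dose lowers the share. The power figures rest also on assumed time-weighted recall and a borrowed dz of 1, and serve only as illustration.

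MAP needs two smaller corrections: its stated purpose does not match this trial, and any response analysis would be diluted. A reader should not conclude that Objective 2 has no acute self-report of anhedonia. SHAPS is one, provided it is completed after the dose. This is a cheap improvement, not a threat to the trial's main conclusions.

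**What to change.** 1. In section 4 (Objective 2 dependent variables) and section 7 (Analytic Strategy, Objective 2), name SHAPS for anhedonia, POMS and STAI State as the acute self-report outcomes. Use BDI Anhedonia only as a baseline descriptor or predictor.
2. In the MAP entry in section 5, replace the inflammation-blockade purpose with one that fits this trial. If MAP is analysed for response, label it exploratory and note its 24-hour window.
3. Reconcile the Study Overview in section 5 with Objective 2 and its analysis, so that the state scales are completed after the dose as well as before it. Without this, the first change gains nothing.
4. State the recall periods of the IDS-SR and MFI versions in use, so that their role can be settled on the same basis.

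The cost is mainly wording, plus a post-dose sitting for the state scales if none is now held. The one loss is a secondary self-report subscale as a response outcome, which SHAPS already covers as a state.

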### **Neurocognitive Assessments:**

A range of neuropsychological assessments will be used to probe basal ganglia function and will be associated with inflammation status as noted above. Assessments will lie along a continuum, progressing from more purely motor tasks (such as finger tapping) which assess circuitry within the basal ganglia to those that involve motor speed with increasing cognitive demand and cortical participation (e.g. the Digit Symbol Task). In addition, we will administer a test of procedural memory, with minimal processing speed or reaction time demands, that has been shown to be sensitive to dysfunction in the basal ganglia, without the executive demands associated with tests of frontal lobe function. Every effort will be made to match groups on the basis of demographic factors affecting test performance, such as age, education level, gender and ethnicity. These factors can significantly influence neuropsychological test results and while relatively small variations between groups can be handled through addition of covariates to statistical analyses, more significant differences in group composition will threaten the integrity and interpretation of the results.

**Finger Tapping Task (FTT):** This task uses a specially adapted tapper that the subject is asked to tap as fast as possible using the index finger. The subject is given 5 consecutive 10-second trials for both the preferred and non-preferred hands. The finger tapping score is the mean of the 5 trials and is computed for each hand. Performance norms have been established, and scores have been shown to be stable over time (84). The FTT is designed to assess subtle motor impairment and has been found to be altered in subjects with basal ganglia disorders and lesions (85).

**Reaction Time Task (CANTAB):** The reaction time test includes simple and choice reaction time tasks and is

divided into 5 stages requiring increasingly complex chains of responses and providing distinction between reaction (or decision) time and movement latencies. Movement times on the CANTAB reaction time task have been shown to be slowed during IFN- $\alpha$  treatment and correlate with IFN- $\alpha$ -induced depression and fatigue (see Preliminary Results). Moreover, reduced DA transmission, as indicated by increased binding of the dopamine D2/3 ligand I-ZBM in the striatum, has been correlated with motor slowing in the CANTAB reaction time task in depressed patients (86).

**Choice Reaction Task (CANTAB):** (87): **Variables:** Reaction Time, Movement time. Speed and accuracy in responses upon being instructed to choose one among multiple stimuli flashed on a computer screen.

**Delayed Matching To Sample (CANTAB):** (88, 89) **Variables:** Response time, Discrimination (Hits/False Alarms). A measure of visual memory where subjects are asked to identify objects shown previously at various time points.

**Spatial Working Memory (CANTAB):** (90) **Variables:** Response time, Correct responses. A test of ability to remember spatial localization of objects presented previously.

**Trail Making Tests A and B (TMT)** is a commonly used neuropsychological measure with updated norms. Part A (TMT-A) requires the patient to connect numbered circles in order and reflects a measure of basic attention and processing speed. Part B (TMT-B) requires the patient to connect alternating letter-number sequencing circles in order and reflects basic attention and processing speed.

**Digit Symbol Task:** The Digit Symbol Task is a subtest of the Wechsler Adult Intelligence Scale (WAIS) and consists of rows of blank squares, each printed with a randomly assigned number (1-9). A key is printed above these rows and shows each number paired with a different nonsense symbol. The subject's task is to fill in the blanks with the corresponding symbols as rapidly as possible. This test involves graphimotor speed, visual scanning and memory, with about half of the variance being accounted for by graphimotor speed, a third by visual scanning and 4-5% by memory (91). As part of the WAIS, this test is frequently used in neuropsychology and relevant norms and test-retest reliability have been well established (84). Performance on the Digit Symbol Test has been found to correlate with subcortical atrophy (esp. as measured by the bi-caudate ratio) in disorders involving the basal ganglia including Huntington's disease and multiple sclerosis (92, 93).

**Effort-Expenditure for Rewards Task (EEfRT):** In this effort-discounting variant (Treadway et al., 2009), subjects are presented with a choice between two task-difficulty levels in order to obtain monetary rewards. In each trial, subjects must make repeated manual button presses within a certain period of time. To succeed in each trial, subjects must meet or exceed the required number of button presses within the time allotted. Easy-task trials require 30 button presses within 7 seconds, while hard-task trials require 99 button presses within or before 21 seconds have passed. There are also probability cues attached to each trial—88%, 50%, and 12%—that determine whether a trial may result in compensation, upon completion. This information will be made known to the subjects at the start of the task. Upon completion of all trials, two of the trials will be selected and the subject will receive compensation from those trials based on the choices they made. This payment may range from approximately \$0.00- \$60. This task lasts approximately 15 minutes, and the number of trials subjects complete is based on their choices and button press rate.

**Stroop Color and Word Test:** Subject is requested to name the color of a word both when the color of the ink matches the name of the color and when the color of the ink does not match the name of the color.

Prolongation in reaction time and number of inaccurate responses during the name-ink color mismatch condition are measured.

**Rey Auditory Verbal Learning Test (RAVLT):** A test of verbal memory and learning using list learning that measures ability to use strategies to improve learning.

**Reliability of ratings:** All clinicians performing the SCID in this study will be trained to conduct the assessments according to standardized guidelines for the administration of the instrument and will conduct interim training sessions to maintain standardization of ratings. In addition, training on the HDRS and SANS will be provided for relevant study personnel, and interrater reliability will be established. Trained staff will conduct the neurocognitive assessments. New staff joining the study team will go through an apprenticeship for the ratings and training for reliability prior to performing independent ratings.

**MRI Neuroimaging:** MRI experiments will be conducted on a 3T Siemens Trio MRI scanner at any of the Emory Imaging Facilities. The patients will be informed of the time requirements prior to participation in the

study. All subjects will be required to limit caffeine intake for two hours prior to the scan. Any food or drink intake during this time frame will be recorded using a MRI Scan Food, Drink and Cigarette Intake Form immediately prior to the fMRI scan. MRI scans do not expose patients to radiation or any invasive procedures; however, MRI scanning can affect metallic and other implants. All subjects will be carefully screened for metallic implants and other contra-indications to MRI prior to the procedure, using the standard Emory University Biomedical Information Technology Center MRI screening form. The subject will be pre-screened with the "MRI Screening form" to confirm MRI safety per protocol prior to each scan session. Subjects with contra-indications will not receive a MRI scan. The MRI scanner is an enclosed space and subjects may experience claustrophobia while being scanned. Should a subject develop claustrophobia during the procedure, the scan will be terminated. Patients may also be invited to participate in additional scans on a voluntary basis. The first scan session will occur at study Visit 1, and will include task-based and resting-state fMRI, as well as high resolution anatomical T1 MRI, which will be performed as one continuous procedure. Scans will include resting-state fMRI and ASL scans that will occur before and after administration of L-DOPA or placebo.

Anatomic images: will be obtained using a T1 weighted MPRAGE sequence with the following parameters: TR/TI/TE =2500/1100/3.02 ms; 8° flip angle; FOV of 256×224×192 mm^3; matrix of 256×224×192; 1 mm thickness; GRAPPA 2; total scan time will be 6 minutes. A diffusion tensor imaging (DTI) sequence will also be acquired during the first scan of the initial visit using 128×128 matrix; FOV = 256×256 mm^2; resolution = 2 × 2 × 2 mm^3; parallel imaging with a GRAPPA factor of 2, BW =1954 Hz/pixel, 64 slices, TR/TE = 8700/98 Ms; total scan time will be 12 minutes.

Resting-state fMRI: Images for functional connectivity will be acquired with a 9 minute Z-SAGA sequence to minimize artifacts in the frontal cortex due to sinus cavities. During the resting-state scan, participants will be instructed to lie passively in the scanner and to focus on crosshairs. Image preprocessing will follow standard steps for resting-state fMRI using AFNI software (NIMH, USA). A series of conventional anatomical scans will be obtained for each subject allowing the subsequent superposition of voxels or regions of interest. Regions of interest in ventral and dorsal striatum will be corroborated by regions activated in the task-based fMRI (see MIDT below).

Arterial Spin Labeling (ASL) for Cerebral Blood Flow (CBF): The CBF pre- and post-L-DOPA or placebo administration will be monitored with a 4.5 minute resting scan sequence using a single readout stand-alone SE CBF sequence acquired 5 ascending slices (TR of 4500 ms, 3.43 × 3.43 × 5 mm resolution with 75% partial Fourier acquisition and a TE of 27 ms).

Diffusion Tensor Imaging (DTI): Chronic exposure to increased inflammation may have long-term consequences on brain circuitry, including degeneration of white matter fiber tracts that are necessary to maintain neural connections.(94) Therefore, DTI will be collected at the initial scan to determine whether decreased structural connectivity in key basal ganglia outflow tracts predict or potentially confound responses to L-DOPA. Diffusion weighted images will be obtained using double spin-echo EPI sequence with settings of FOV = 224×224 mm; resolution=1.8×1.8×1.8 mm; flip angle=78°; parallel imaging with a GRAPPA factor 2; bandwidth=1776 Hz/pixel; number of slices=81; slice thickness=1.75mm isotropic; TR/TE=3430/90 ms; GRAPPA accelerated PE=2; multiband accelerating factor=3; EPI factor=128 with a duration of 8.17 minutes.

Task-based fMRI - Faces Task: This is a task that has been developed to measure brain activity in response to viewing of fearful and neutral faces. For the duration of the task, patients will be instructed to passively view faces as they appear on the screen. The task lasts 5 minutes and proceeds as follows: 15 blocks of 16 trial face stimuli are presented in pseudorandom order. Each block contains 8 fearful faces and 8 neutral faces presented in random order. Each face stimulus is presented for 500ms, followed by a 500ms presentation of a fixation cross. After every 10th block, a 10,000ms rest period is presented. The task has been designed to minimize patient discomfort and enhance cooperation. If at any time a patient experiences negative or unpleasant reaction, they will be removed from the scanner. The addition of these tests does not add to the overall risk to patient safety.

**Task-based fMRI - Modified Monetary Incentive Delay Task (MIDT):** This is a task that has been developed to measure behavioral and brain changes in response to reward and non-reward situations. Prior to entering the scanner, the patient will practice the MIDT on a laptop computer for approximately 15 minutes to ensure they understand task instructions. Reaction times for each practice trial will be recorded; the in-scanner MIDT is adapted to each patient's reaction time to ensure that each patient wins or fails to lose on ~66% of trials. The in-scanner session lasts 12 minutes and proceeds as follows: 1) Patient is shown 3 possible phrases that indicate monetary rewards of win (+\$), loss (-\$) or no change. 2) Patient is instructed to press a button as quickly as possible. 3) If the patient presses the button within a pre-specified time frame (based on their practice trials), they win or do not lose money. This message appears on the screen. Cumulative winnings (average of ~\$2) are also shown after each trial. Patients are paid 1/3 of their cumulative winnings (up to \$20), and are instructed of this during the consent process. The task has been designed to minimize patient discomfort and enhance cooperation. If anytime the patient experiences negative or unpleasant reaction, they will be removed from the scanner. The addition of these tests does not add to the overall risk to patient safety.

**Baseline Assessments:** During screening, a research blood sample (18 ml total) may be collected along with blood draw for safety labs and/or CRP measurement. Research blood will be used for measurement of plasma inflammatory markers, mRNA gene expression for inflammatory signaling pathways, circulating and mRNA gene expression markers related to metabolism and endocrine hormones, and buffy coat to examine polymorphisms in relevant inflammatory proteins. For female subjects, questions pertaining to menopausal status will also be obtained using a Staging System for Reproductive Aging questionnaire. All patients will also complete a Composite Vascular Risk Profile Scale. A complete series of neurocognitive testing may also be performed during the last screening visit or the LP visit. The baseline research blood and neurocognitive assessments are necessary to complete prior to randomization to study treatment. They may be collected along with screening assessments that are being conducted to determine eligibility for the LP procedure or randomization to study drug, or at the LP visit. Physiological measures including heart rate and activity may also be recorded using adhesive ECG patches. These data may also be used independently of qualification for further study participation. To reduce patient burden, a 15 minute break will be given in between motivational and motor assessments. Participants will receive \$25 for this visit, an additional \$25 if research blood is collected, and an additional \$25 if ECG patches are placed. Patients will also receive \$50 for completing motor and motivational assessments, and up to \$60 for completing the EEfRT based upon the subject's responses.

**ECG patches for collection of biometric data (optional):** Patients will be given the option of wearing ECG patches (MC10 BioStamp®) to record physiological measures including heart rate and activity. Trained members of the study team will place the ECG patches on the chest of the subject and they will record heart rate and activity over 24 hours. Another patch may need to be placed on the subject's leg; the subject will be trained to do this themselves. These patches will be returned to the study team either at the next study visit or by a pre-paid envelope that will be provided to the subject.

**Lumbar Puncture (LP):** Patients will have a LP performed by an Emory Anesthesiologist between 7am-12 pm following hydration with approximately ~1 liter of fluid IV as a result of a KVO (keep vein open) flow of normal saline through the indwelling catheter. This administration of IV fluids has been found in our experience to markedly reduce the incidence of post-LP headache. It will also help standardize hydration levels between subjects. An experienced Emory attending anesthesiologist will perform/supervise the LP using standard sterile technique and local anesthesia with patients in the lateral decubitus position. The subject will be given the option to receive a pre-LP sedation (versed) through IV prior to the LP procedure by the anesthesiologist. Approximately 11 cc of CSF will be withdrawn. After discarding the initial 1 ml (to avoid blood contamination), the remaining CSF will be collected into chilled tubes and aliquoted on ice in 1 ml eppendorf tubes, which will be immediately frozen at -80 C for later batched analyses. Upon completion of the LP, subjects will lie flat for approximately one hour and subsequently discharged after 4 hours. Some patients experience some lower back pain after a lumbar puncture. This is usually felt in and around the area where the needle was inserted. In most cases the pain will ease after a few days and it can be treated with analgesics, such as acetaminophen, if necessary. If subjects develop a headache they will be treated with pain medication or the application of a

blood patch. Subjects will be instructed to have a family member or friend be present to transport them home from the ACTSI Unit following the LP procedure. Patients will receive \$500 for participating in the LP procedure.

**Study Visit 1 & 2 (L-DOPA or placebo administration):** To determine whether increasing dopamine release in the basal ganglia with L-DOPA (250 mg with carbidopa 50 mg, also referred to as Sinemet) can reverse the neurobiological changes associated with increased inflammation observed in resting-state fMRI scans. Participants will complete two, 1 day visits (approximately 5-6 hours in duration) based in the EUH CRN or in the Behavioral Immunology Program offices in the Emory Clinic, Building B, and the Emory Neuroimaging Facilities. An anatomical and functional connectivity MRI scan that will last approximately 25-35 minutes will be performed before administration of L-DOPA or placebo (double-blind, randomized by Emory IDS), which will be administered by the study physician or a designated Nurse Practitioner. Vital signs will be monitored before, during, and after administration. A post-treatment scan, including the Monetary Incentive Delay Task (MIDT), will be performed ~45 minutes following administration of L-DOPA and will last approximately 45-55 minutes. Because protein may reduce absorption of L-DOPA, subjects will be asked to eat a light breakfast and not to consume any food within three hours of their scans (water and juices are allowed) and to limit caffeine intake for 2 hours prior to the scan. A low protein snack may be offered by the study team to the participant prior to administration of the L-DOPA or placebo. Participants may also be offered up to 30mL of Maalox (aluminum hydroxide/magnesium hydroxide/simethicone) after scan 2 to prevent nausea. The MRI scans will be conducted as described above as one continuous acquisition (see T1 anatomical, resting-state fMRI, MIDT and ASL protocols). Patients may also undergo a clinical interview if it has been >2 weeks since their last psychiatric assessment, and will be asked to complete self-report questionnaires related to their mood and will be administered objective tests of motivation and psychomotor speed. A blood sample (6 ml total) will be collected into EDTA tubes immediately after the final scan to measure pharmacokinetic parameters of L-DOPA. Participants will be discharged by the CRN staff or the study physician after assessment of vital signs and neurological status including coordination and sedation. Patients can receive up to \$280 for completion of each study visit including an extra \$20 in winnings from the MIDT and a maximum of \$60 for completing the EEfRT.

